### **7.5. Minimum Inhibitory Concentrations**

Minimum inhibitory Concentrations (MICs) for all drugs will be tabulated separately. Baseline will be cross tabulated against end of treatment. If measured at multiple visits, end of treatment will be used. This is for descriptive purposes only.

## **8. Safety Statistical Analysis**

All safety endpoints will be presented descriptively, and no inferential tests will be carried out. AE duration will be calculated as (Stop Date – Start Date) + 1. Partial dates for AEs will not be imputed. In the case where it is not possible to define an AE as treatment-emergent or not, the AE will be classified as treatment-emergent.

At each level of participant summarisation, a participant is counted once within each PT and then each SOC if the participant reports one or more events.

### **8.1. All-cause mortality**

A table will be presented that contains the cause of death as well as the following details about death (Yes/No):

- Death was related to TB
- Death due to treatment failure
- Death was violent or accidental (excluding suicide)
- Death was due to suicide

### **8.2. Treatment emergent AEs (TEAEs)**

#### **8.2.1. Incidence of TEAEs**

Summaries of the total number of TEAEs and the number and percentage of participants with at least one TEAE will be provided.

### **8.2.2. Severity**

A summary of TEAEs by maximum severity will be presented in a table. In the TEAE severity table, if a participant reported multiple occurrences of the same TEAE, only the most severe TEAE is presented. TEAEs that are missing severity will be presented in tables as 'Severe' but will be presented in the data listing with a missing severity. A separate table will be presented for 'Grade 3: Severe' or 'Grade 4: Potentially life-threatening' TEAEs.

### **8.2.3. Drug-related TEAEs**

A summary of TEAEs by relationship to study treatment will be presented in a table by incidence of occurrence. The investigator will provide an assessment of the relationship of the event to the study treatment and specifically for bedaquiline, pretomanid, moxifloxacin, pyrazinamide, and HRZE/HR. The possible relationships are summarised as 'Not Related' (i.e. 'Not Applicable', 'Not related', 'Unlikely') and 'Related' (i.e. 'Possibly', 'Probably', and 'Certainly') in the table and their actual values (i.e. 'Not Applicable', 'Not related', 'Unlikely', 'Possibly', 'Probably', and 'Certainly') in the listing. In the TEAE relationship table, if a participant reports multiple occurrences of the same TEAE, only the most closely related occurrence will be presented. All TEAEs that have a missing relationship will be presented in the summary table as "Certainly" but will be presented in the data listing with a missing relationship.

### **8.2.4. Serious TEAEs**

Treatment-emergent SAEs will be categorised and presented by SOC and PT in the same manner to that described in §8.2.1. The same summary will be repeated for Bedaquiline, Pretomanid, Moxifloxacin and Pyrazinamide separately.

### **8.2.5. TEAEs leading to treatment discontinuation or interruption**

A summary of TEAEs with action taken with study treatment as 'Permanently Discontinued' for BPaMZ or HRZE/HR will be presented in a table. At each level of participant summarisation, a participant is counted once if the participant reported one or more events.

The same presentation will be provided for interruption of BPaMZ or HRZE/HR ('Action Taken with IMP' is 'Interrupted'). Data will be categorised and presented by SOC and PT in the same manner to that described in §8.2.1.

### **8.2.6. TEAE leading to study discontinuation**

A summary of TEAEs where the answer to action taken' is 'Withdrawn from Study' will be presented in a table. At each level of participant summarisation, a participant is counted once if the participant reported one or more events. Data will be categorised and presented by SOC and PT in the same manner to that described in §8.2.1.

### **8.2.7. TEAEs leading to death**

A summary of TEAEs where the answer to 'Outcome' in the AE form is 'Fatal' will be presented in a table. Data will be categorized and presented by SOC and PT in the same manner to that described in §8.2.1.

### **8.2.8. Liver-related TEAE**

A summary of TEAEs that has preferred terms under “Hepatic disorders” according to MedDRA dictionary will be presented by SOC and PT in the same manner to that described in §8.2.1. In addition, any liver-related TEAE tables will be presented by region, sex, age (< vs. >median), previous alcohol intake and HIV status.

#### **8.2.8.1. Liver and drug-related TEAEs**

A summary of liver-related TEAEs that are drug related (i.e. ‘Possibly’, ‘Probably’, and ‘Certainly’) will be presented by SOC and PT for treatment arm and drug in the same manner to that described in §8.2.1.

#### **8.2.8.2. Serious liver-related TEAEs**

A summary of TEAEs that are liver related and serious (as described in § 2.3.2.4) will be presented by SOC and PT for treatment arm in the same manner to that described in §8.2.1. Liver enzyme profile plots will be provided for patients with treatment emergent serious adverse events that have toxicity grade 3 or higher for either AST, ALT, ALP or total bilirubin.

#### **8.2.8.3. Incidence of hepatotoxicity**

Proportion of participants experiencing at least one liver function test (LFT; AST or ALT) that is  $\geq 3$  x ULN or at least one hepatic SAE (as described in §8.2.8). This will be summarised in a table by treatment arm (and combining the BPaMZ arms to give a BPaMZ total). In addition we will summarise for those who have had a hepatotoxicity what their hepatitis status (A, B and C) was at baseline, at the time of the event and the change from baseline to time of event.

#### **8.2.8.4. Predictors of hepatotoxicity**

As an exploratory analysis, pending numbers, predictors of having a hepatotoxicity (binary outcome of at least one LFT  $\geq 3$ xULN or not) will be investigated. Potential predictors will include, but are not limited to, baseline variables (see §7.4 with the addition of weight and BMI) and hepatitis (A, B or C) at baseline. Logistic regression will be used for this binary outcome. If this logistic regression analysis converges and shows any suggestion of a predictor then, pending numbers in each group an ordered logistic regression will be considered using the outcomes as described in Table 3 which lists notable criteria for AST and ALT. If there are no or very small numbers of patients with  $\geq 8$ xULN then this may be combined with the  $\geq 5$ - $<8$ xULN group.

### **8.2.9. Additional TEAE summary**

The number and percentage of participants with the following specific TEAEs will be presented: grade 2, 3, or 4 myalgia, and grade 3 or 4 cardiac rhythm disturbances, grade 3 or 4 lipase, pancreatitis, peripheral neuropathy.

All AEs will be presented in a listing, which will specify whether they are treatment emergent or not.

## **8.3. Clinical Evaluation**

### **8.3.1. Clinical Laboratory Evaluation**

A list of laboratory tests (haematology, clinical chemistry, and urinalysis) to be included in the analysis is presented in [§7.3 of the protocol](#). Laboratory assessments done by a central laboratory will be summarised in tables. All summaries will be based on the units provided by the central laboratory, no conversion will be done. The laboratory evaluations will be summarised for baseline, post-baseline, and change from baseline at week 8, end of treatment (week 17 or week 26), 52 week and 104 week FU.

Laboratory values outside normal ranges will be identified, and the number and percentage of participants with at least one post-baseline abnormality will be summarised in shift tables comparing the baseline results to each post-baseline timepoint for those participants with results at both timepoints.

The table below displays the general variables and thresholds of interest. Participants are considered to have notable laboratory abnormalities if his/her response falls within the specified definitions at least once during the treatment period.

Table 3:Notable Criteria for Laboratory Data

Lab Test Type	Laboratory Variable	SI Units
Liver	AST	>3 x ULN and ≤ 5 x ULN >5 x ULN and ≤ 8 x ULN >8 x ULN
	ALT	>3 x ULN and ≤ 5 x ULN >5 x ULN and ≤ 8 x ULN >8 x ULN
	Total Bilirubin	>2 x ULN
	Alkaline Phosphatase (ALP)	>2 x ULN
Chemistry Labs	Other: ALT or AST > 3 x ULN and total bilirubin > 2 x ULN ALT or AST > 3 x ULN and total bilirubin > 2 x ULN and ALP < 2 x ULN (potential Hy's law case)	
	Lipase	>2xULN to ≤5XULN >5xULN

### 8.3.2. Vital Sign Measurements

Vital sign measurements include blood pressures (mmHg) (resting more than 5 minutes), and heart rate (bpm). These measurements will be summarised for baseline and change from baseline at week 8, end of treatment (week 17 or week 26), 12 and 24 month follow-up. Only the vital signs collected at the scheduled visits or time points will be included in the summary.

Abnormal vital sign assessment results will be identified, and the number and percentage of participants with at least one post-baseline abnormality will be summarised. General variables and thresholds of interest are outlined in [appendix 3 of the protocol](#).

#### **8.4. Electrocardiogram**

All participants will have a standard 12-lead (ECG) assessment (heart rate (HeR), PR interval, RR interval, corrected QTcF intervals (adjusted using Fridericia's correction) performed by a central cardiologist. All summaries will be based on the central cardiologist assessment.

For all ECG parameters (HeR, PR, RR, QTcF), actual values and changes from measurement closest to and prior to dosing at each time point (week 8, end of treatment (week 17 or week 26), week 39 will be summarised using descriptive statistics by treatment group and time of collection.

Post-baseline QTcF intervals will be classified into the following categories:

- QTcF  $\leq$  450 msec
- 450 msec  $<$  QTcF  $\leq$  480 msec
- 480 msec  $<$  QTcF  $\leq$  500 msec
- QTcF  $>$  500 msec

QTcF changes from baseline will be classified into the following categories:

- increase  $>$  0 msec and  $\leq$  30 msec,
- increase  $>$  30 msec and  $\leq$  60 msec, and
- increase  $>$  60 msec.

Number and percentage of notable maximum QTcF interval and change from baseline QTcF interval will be summarised.

Interpreted ECG results based on CRF investigator assessment will be classified as "normal", "abnormal, not clinically significant", or "abnormal, clinically significant". The number and percentages of participants with normal, abnormal not clinically significant, and abnormal clinically significant will be presented. In addition, shift tables will be provided to summarise the status changes from baseline to week 8, end of treatment, 12 and 24 month follow-up assessments.

Patients with any QT or QTcF values  $\geq$  500 that resulted in early withdrawal will be presented in a figure.

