### **2.3.4. Electrocardiogram**

The electrocardiogram (ECG) results (heart rate, RR interval, PR interval, QRS interval, QT interval and QTc interval), which are read by a central cardiology service, observed measurements and change from baseline. QT/QTc intervals, maximum change from baseline, will be categorised according to §8.4 below. The ECG results will be considered at baseline, week 8, week 17, week 26, week 39 and early withdrawal in all participants.

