### **2.3.5. Changes in male reproductive hormones**

The change in male reproductive hormones (testosterone, follicle-stimulating hormone (FSH), luteinizing hormone (LH) and Inhibin B) for all male participants in all treatment groups from baseline to end of treatment visit (week 17 or week 26 depending on treatment group) and week 39.

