### **3.6. Trial Timings**

Study Day 1 is defined as the date on which a participant is administered the first dose of the study medication. Other study days are defined relative to the Study Day 1 with Day 2 being the day after Study Day 1 and Day -1 being the day prior to Study Day 1.

For all safety endpoints, baseline is defined as the last non-missing measurement prior to first dose of study treatment unless otherwise stated.

In all analyses, visit date rather than day or week number will be used to define the timing of events. For participants treated with the 6-month regimens (HRZE/HR for DS-TB participants and 6mBPaMZ for DR-TB participants) this will be taken as a total of 26 weeks, i.e. 182 dosing days. For DS-TB participants randomised to 4 months of BPaMZ a total of 17 weeks (119 dosing days) is taken. As per the protocol, assessments should be collected as follows:

- Within  $\pm 3$  days of scheduled visit from day 1 to week 8
- Within  $\pm 5$  days of scheduled visit from week 12 to week 26
- Within  $\pm 14$  days of scheduled visit during the follow-up phase at or after month 6 to month 24.

Unscheduled visits and visits outside of these windows will be slotted into windows as appropriate. Visits falling outside of the defined protocol visit windows will be put into separate visits so that all data, both collected at scheduled and unscheduled time points, are used.

The **treatment period** is defined as either 17 or 26 weeks from start of therapy depending on allocated treatment regimen.

The **follow-up period** is defined as the period after the end of treatment to the end of follow-up.

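### The ECG by-visit tables in SAP section 8.4 leave out time points and parameters that section 2.3.4 makes part of the outcome, and set week 17 of 4BPaMZ beside week 26 of HRZE/HR

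*SAP*

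**What the plan says.** Section 2.3.4 sets the outcome. The parameters are "heart rate, RR interval, PR interval, QRS interval, QT interval and QTc interval", read centrally. The time points are explicit: "The ECG results will be considered at baseline, week 8, week 17, week 26, week 39 and early withdrawal in all participants". It adds that the maximum change in QT and QTc will be categorised as section 8.4 describes.

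Section 8.4 sets the analysis. It opens with "For all ECG parameters (HeR, PR, RR, QTcF), actual values and changes from measurement closest to and prior to dosing" and continues "at each time point (week 8, end of treatment (week 17 or week 26), week 39 will be summarised using descriptive statistics by treatment group". It then classifies post-baseline QTcF into four bands and QTcF increases into three bands, and summarises the maximum QTcF and the change from baseline. It also plans a figure for participants whose QT or QTcF of 500 or more led to early withdrawal.

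A separate part of section 8.4 takes the investigator's normal/abnormal reading from the CRF. For that reading, "shift tables will be provided to summarise the status changes from baseline to week 8, end of treatment, 12 and 24 month follow-up assessments".

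Section 3.6 makes the end of treatment depend on the regimen: the treatment period "is defined as either 17 or 26 weeks from start of therapy depending on allocated treatment regimen".

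**The concern.** The two sections describe the same outcome with different visits and different parameters, so a programmer who works from section 8.4 will not produce what section 2.3.4 defines.

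The visits matter most. Section 1 says that 4BPaMZ will be compared with HRZE/HR in all analyses unless otherwise stated. Week 17 is the one ECG after week 8 at which all three groups are scheduled to be on treatment. Week 26 shows 4BPaMZ after scheduled treatment has stopped, while the other two groups are just finishing. A single end-of-treatment row gives neither view. Instead it sets one arm at week 17 beside the other at week 26, so a difference in QTcF change between arms is mixed with a difference in time since randomisation.

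Early withdrawal is named in the outcome but has no row in the by-visit tables.

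**Working it through.** No power or sample-size figure is involved. The check is a side-by-side reading with simple counts.

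| Item | Section 2.3.4 (outcome) | Section 8.4 (values and changes) |
|---|---|---|
| Week 8 | all participants | all arms |
| Week 17 | all participants | 4BPaMZ only, as end of treatment |
| Week 26 | all participants | HRZE/HR and 6BPaMZ only, as end of treatment |
| Week 39 | all participants | all arms |
| Early withdrawal | all participants | no row |
| Heart rate, PR, RR | listed | listed |
| QTc | listed | listed, as QTcF |
| QRS, QT | listed | not listed |

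**Which week is end of treatment.** From section 1.1, 4BPaMZ has 8 + 9 = 17 weeks of treatment, HRZE/HR has 8 + 18 = 26, and 6BPaMZ has 8 + 18 = 26. Section 3.6 agrees.

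**Gap within the end-of-treatment row.** 26 − 17 = 9 weeks between 4BPaMZ and HRZE/HR.

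**Scheduled ECGs omitted.** Section 2.3.4 has four scheduled post-baseline weeks (8, 17, 26, 39). Section 8.4 uses three of them for any one participant, so 4 − 3 = 1 is missing from the by-visit tables: week 26 in 4BPaMZ, and week 17 in the other two groups.

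**What the retained visits can show.** At week 8 every arm is on treatment. At week 39 none is: 4BPaMZ is 39 − 17 = 22 weeks past its scheduled end, and the others are 39 − 26 = 13 weeks past theirs. Neither visit stands in for a same-week view at 17 or 26.

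**Is the separate listing of weeks 17 and 26 a slip?** Probably not. The next outcome, male hormones in section 2.3.5, uses the arm-specific form, "end of treatment visit (week 17 or week 26 depending on treatment group) and week 39", and section 2.3.6 on lens opacity also uses either-or wording. Section 2.3.4 does not: it lists both weeks and applies them to everyone.

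**QTcF change bands.** They run from above 0 to 30, above 30 to 60, and above 60 msec. A participant with no change or a decrease falls in none of them.

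**The case against.** The strongest reply is that little is really lost, and much of it stands.

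- A reader might infer that section 8.4 discards every visit except end of treatment, or that same-week QTcF comparison disappears altogether. The document does not support this. Weeks 8 and 39 are kept as same-week summaries in every arm.
- A reader might also infer that the omitted week-17, week-26 and early-withdrawal ECGs drop out of the analysis, so that a QT problem could go unseen. That does not follow. The QTcF bands and the maximum are not tied to a visit and can include those ECGs. Section 3.6 aims to use data from scheduled and unscheduled visits alike, and the figure covers values of 500 or more that led to withdrawal. QT is not wholly absent either, since that figure uses it.
- The shift tables cover "status changes from baseline to week 8, end of treatment, 12 and 24 month follow-up assessments". Section 2.3.4 does not list months 12 and 24, and the tables omit week 39. It is tempting to count this as part of the QTcF loss, but the tables use the investigator's reading, which is a different data source. Whether ECGs are taken at those months depends on the protocol schedule, which is not available here.
- All safety output is descriptive (sections 2.3 and 8), 6BPaMZ is not randomised, and section 1 plans no formal comparison for it. An end-of-treatment row is also the plan's usual safety convention.

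One further argument does not succeed. Section 8.4 summarises by time of collection and never says that its visits are the only ones, so both sections could be satisfied by adding rows. But the time points are enumerated immediately before that phrase, and the enumeration merges weeks 17 and 26. Adding the rows is the correction, and the text does not now call for them.

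**Conclusion.** The point holds as an internal contradiction: section 8.4 is wrong as written against the plan's own outcome definition. Severity is minor.

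Its extent is one of four scheduled post-baseline ECGs per participant missing from the by-visit tables, no early-withdrawal row, QRS and QT not summarised, and a nine-week mismatch between the randomised arms in the end-of-treatment row. The by-visit tables lose the only same-week, on-treatment contrast after week 8. The category and maximum tables are not restricted by visit, and no test or decision rule changes.

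This rests on two assumptions: that end of treatment in section 8.4 carries the regimen-specific meaning of sections 2.3.5 and 3.6, and that participants keep to the scheduled treatment duration. The shift-table visits are a separate question that this document cannot settle.

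**What to change.** In section 8.4:

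- Summarise values and changes for heart rate, PR, RR, QRS, QT and QTcF at weeks 8, 17, 26 and 39 and at early withdrawal, for every arm, to match section 2.3.4. Keep end of treatment as an additional row.
- Add a no-increase row (≤0 msec) to the QTcF change categories so that they cover all participants.
- Separately, reconcile the visits of the investigator-read shift tables with the ECG schedule. Either confirm that ECGs are taken at 12 and 24 months or change the visits, and say whether week 39 belongs there.

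The cost is SAP wording and table shells. The additions to the by-visit tables need no ECG beyond those that section 2.3.4 already lists.

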### **8.5. Male Reproductive Hormone Tests**

Descriptive summary statistics by treatment arm will be presented for each of testosterone, follicle-stimulating hormone, luteinizing hormone, and inhibin B. These will only be presented for those participants who have had these tests carried out at an official timepoint. Any participant who has had these tests carried out outside the official windows will not be included. The timepoints are as follows: screening and baseline (Day 1) results to be displayed together taking the average of the two, end of treatment (week 17 or week 26) and week 39 follow-up. Change from baseline (average of screening and day 1) for each reproductive laboratory parameter will be presented at end of treatment (week 17 or week 26) and 9 month follow-up by treatment arm.

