### **3.3. Adequate Treatment**

The definition of adequate treatment sets a limit for the amount of treatment missed. Participants not taking the adequate amount of treatment by this definition will be excluded from the PP analysis (see [§6.2.3](#)).

Participants allocated to a 4 month regimen, to meet the definition of adequate treatment they must have taken at least 96 doses (80%) of their allocated 119 day (17 weeks) treatment regimen within 175 days of starting therapy (i.e. 17 weeks plus an allowable 56 day halt (including a maximum of 35 consecutive days) as per the protocol).

Participants allocated to a 6 month regimen, to meet the definition of adequate treatment they must have taken at least 146 doses (80%) of their allocated 182 day (26 weeks) treatment regimen within 238 days of starting therapy (i.e. 26 weeks plus an allowable 56 day halt (including a maximum of 35 consecutive days) as per the protocol).

Participants in the control arm are additionally required to have taken at least 80% of their allocated intensive treatment.

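### SAP §8.5 excludes any man with an out-of-window hormone test, which contradicts the all-data rule in §3.6 and the all-males outcome in §2.3.5

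*SAP*

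**What the plan says.** **Hormone outcome.** SAP §2.3.5 defines the change in four male reproductive hormones "for all male participants in all treatment groups from baseline to end of treatment visit" and to week 39.

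**Hormone tables.** SAP §8.5 first gives an inclusion rule: "These will only be presented for those participants who have had these tests carried out at an official timepoint". It follows this with an exclusion rule: "Any participant who has had these tests carried out outside the official windows will not be included". The timepoints are screening and Day 1 averaged as baseline, end of treatment (week 17 or 26), and week 39.

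**General rule on visit timing.** SAP §3.6 gives windows of ±5 days from week 12 to week 26 and ±14 days in follow-up. It then says: "Unscheduled visits and visits outside of these windows will be slotted into windows as appropriate". The next sentence puts visits outside the windows into separate visits "so that all data, both collected at scheduled and unscheduled time points, are used".

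**Vital signs.** SAP §8.3.2 closes its paragraph on baseline and change-from-baseline summaries with: "Only the vital signs collected at the scheduled visits or time points will be included in the summary". A separate paragraph then counts participants with any abnormal reading after baseline and does not say which readings qualify.

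**The concern.** A programmer holding an out-of-window hormone sample has two instructions. §3.6 says to use it; §8.5 says to leave out the man who gave it. The second goes further than the usual in-window restriction, because it is worded for the participant and not for the sample.

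Two things are at stake. The first is the denominator: two competent programmers could produce hormone tables with different numbers of men, and both could point to the SAP. The second is possible selection. Men who miss a visit window may differ from those who do not, and a safety table restricted to perfectly timed men may not describe all the men who were exposed. These tables carry no inference, so completeness is what the reader relies on.

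**Working it through.** The SAP gives no figure to reproduce, so the check sets the rules side by side and applies them to one case. It assumes that the official windows of §8.5 are those of §3.6, since §8.5 defines none.

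**Step 1: one man with one late sample.** Suppose baseline is valid, the end-of-treatment sample is in window, and the week 39 sample is 15 days late, one day beyond the ±14-day window. He could contribute two changes from baseline.

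| Rule applied | End-of-treatment change | Week 39 change | Changes kept |
|---|---|---|---|
| §8.5, exclusion sentence read literally | dropped | dropped | 0 of 2 |
| §8.5, inclusion sentence read per timepoint | kept | dropped | 1 of 2 |
| §3.6 | kept | kept (slotted, or shown as a separate visit) | 2 of 2 |
| §2.3.5 | within the defined outcome | within the defined outcome | 2 of 2 |

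The two adjacent sentences of §8.5 give different answers for the same man, and neither agrees with §3.6 or §2.3.5.

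**Step 2: is an exception provided for?** The baseline definition in §3.6 allows for something different being stated elsewhere. The sentences on out-of-window and unscheduled visits carry no such qualifier, and §8.5 does not say that it overrides them.

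**Step 3: could treatment pauses drive the loss?** §3.3 describes adequate treatment as "17 weeks plus an allowable 56 day halt" for the 4-month regimen, with the same 56 days for the 6-month regimens:

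- 119 + 56 = 175 days
- 182 + 56 = 238 days

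The calendar windows at end of treatment close at about 119 + 5 = 124 days and 182 + 5 = 187 days.

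- If the sample follows a delayed last dose and the window stays at the calendar week, a halt of 6 days already falls outside it: 119 + 6 = 125 > 124, and 182 + 6 = 188 > 187.
- If sampling stays at calendar week 17 or 26, or the window moves with the last dose, a pause shifts nothing and nobody is lost.

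The SAP does not say which applies. It defines the treatment period as 17 or 26 weeks from the start of therapy, but it does not say when the end-of-treatment sample is drawn after a halt.

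**Step 4: vital signs.** The scheduled-only sentence ends the by-visit paragraph, and the abnormality count comes in the next one. The natural reading is that the limit applies only to the by-visit summaries, but the text does not say so. For laboratory data, §2.3.3 and §8.3.1 count a notable abnormality if it occurs at least once during the treatment period. That makes the silence in §8.3.2 worth filling.

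**The case against.** **§8.5 may be a per-timepoint rule.** Its inclusion sentence admits men tested at an official timepoint, and the timepoints are then listed. Read together, the sentences can mean that only the mistimed sample is left out. This is a fair reading and may be what was intended. It does not remove the problem: the exclusion sentence names the participant, and even the milder reading discards data that §3.6 says are used.

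**A specific rule can override a general one.** This is common in analysis plans, but here no override is stated, and §2.3.5 would still need the same qualification.

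**The tables are descriptive.** This stands. SAP §2.3 and §8 rule out inferential tests on safety data, so no test or decision depends on the point.

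**Stronger readings that the SAP does not support.**

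- A reader might infer that men with interrupted treatment are systematically lost. Step 3 shows that this depends on visit scheduling that the SAP does not fix. §3.3 serves the per-protocol definition and does not set safety visits.
- A reader might infer that participants with acute symptoms drop out of the vital-sign tables. They do not: the limit concerns readings, and each participant stays in through the scheduled ones. Scheduled-only by-visit tables are common practice, and treatment-emergent adverse events are tabulated under §8.2 without regard to visit.
- A reader might take §3.6 to say that every analysis uses all data. Its opening, "In all analyses, visit date rather than day or week number will be used to define the timing of events", governs timing. The data-use clause comes later in a sentence of its own, although that clause too is general.

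**Conclusion.** The contradiction between §8.5 and both §3.6 and §2.3.5 is established from the text, as is the tension between the two adjacent sentences of §8.5. On the literal reading, one mistimed sample costs a man all his hormone results. The consequence is a smaller and possibly biased descriptive summary of a secondary safety outcome. No efficacy result or hypothesis test is touched.

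The number of men affected cannot be derived: the SAP gives no rate of out-of-window samples, and any percentage would rest on an assumed rate and an assumed dependence between visits. Selective loss of men with treatment pauses is possible only if end-of-treatment samples follow a delayed last dose while the window stays fixed. The vital-sign wording is a minor ambiguity of scope.

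**What to change.** **§8.5.**

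- Delete the participant-level exclusion and keep every in-window result.
- Handle out-of-window samples under §3.6, stating whether each is slotted into the nominal visit or shown as a separate one. At most, leave only the out-of-window sample out of the by-visit table and list it.
- Give an in-window-only table as a sensitivity analysis.
- State how the end-of-treatment hormone window is defined after a treatment halt, consistently with the treatment period in §3.6.

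**§8.3.2 (clarification).** State that the scheduled-only limit applies to the by-visit and change-from-baseline summaries, and that the count of participants with an abnormal reading uses any post-baseline reading, scheduled or not.

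**Cost.** A few sentences of SAP wording and minor programming. The small downside is more spread in sampling times at each nominal visit, which the in-window table would show.
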